Once a subject is identified a page will be sent to a member of the research team (i.e. ED screener, research staff member, GI fellow on call, or GI attending on call) from the ED. In addition to this, the clinical research coordinator and or GI fellow will screen the Emergency Department triage software for patients who are listed as having NHGIB. Based on prior experience Ref Sachdev we expect for every 3 patients asked to participate in the study, there will be 1 patient who agrees to participate. In the emergency department study already cited, the Emergency Department at UMass sees about 350 patients annually for GI bleeding. Of these patients, approximately 230 patients have NHGIB. Given the 3:1 screening ratio, we would expect approximately 75 NHGIB patients every year to agree to participate in the study. In 24 months, we would expect to recruit up to 160 patients to our study.

INVESTIGATOR STUDY PLAN - REQUIRED

Once a subject is identified the subject will then be seen and examined by the GI fellow and attending as per standard of care and asked to participate in the study

Randomization

If inclusion/exclusion criteria are met, the consent discussion takes place and only if the subject agrees and consent is obtained, then the subject is randomized to the “Early Capsule Group” or “Conventional workup Group.” All patients in the “Early Capsule group” will receive the video capsule. Only some of the patients in the “Conventional Workup Group” will receive the capsule as indicated by what is considered the standard workup.

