Depending on the findings a recommendation will be made as to the next most appropriate test. See attached Figure 1. If blood is found in the esophagus, stomach or duodenum an upper endoscopy is recommended. If blood is seen in the small intestine, it will be recommended that the subject next have a push enteroscopy, deep enteroscopy, or angiography. If blood in right colon, colonoscopy may be performed or deferred to colonoscopy as an outpatient, if active bleeding has ceased. If the capsule study is not diagnostic and no blood is seen in the GI tract and there is no ongoing hematochezia, the subject will be placed in ED observation for up to 23 hours and evaluated for potential discharge and follow-up by gastroenterology as an outpatient.

INVESTIGATOR STUDY PLAN - REQUIRED

If no bleeding/ blood or a likely source is found. These individuals will be considered for observation, early discharge and follow up in the GI outpatient setting.

For most subjects, the capsule will pass in a bowel movement within 24 - 72 hours of ingestion.

An equal number subjects [up to 80] will be randomized to the “conventional workup group”. “Conventional Workup” for NHGIB could include upper endoscopy, colonoscopy, and additional capsule or small bowel enteroscopy depending on the subject’s presentation and the results of the workup performed by the gastroenterology team. For some subjects, the VCE would be done as part of standard of care estimated that 5-15% of patients will have small intestinal bleeding. For patients requiring a video capsule endoscopy as part of “conventional workup” the patients will be given the same Olympus video capsule that is used in the “Early Capsule” group. Further management would be as standard of care. These subjects will be discharged on the recommendation of the attending hospitalist after completion of treatment.

Review and Follow-Up

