During hospitalization, data will be recorded from ED pulse check, Meditech, Soarian, and Allscripts regarding fluid administration, transfusion of pRBC, initial hematocrit, times and types of procedures (e.g. upper endoscopy, enteroscopy, colonoscopy), time from entry to ED to time to diagnosis (i.e. localization of source of bleeding), admission disposition (i.e. clinical decision unit, regular floor, ICU), time of discharge. The procedures involved in the hospitalization (i.e. upper endoscopy, enteroscopy, and colonoscopy) will be done as part of standard of care. All of this information will be linked to the subject’s study ID number as described above. This data collection is for research purposes only.

In addition, the costs of the procedures will be collected through financial services. The costs that will be collected are both the fixed and variable costs associated with each patient in the study. We will also collect the direct and indirect costs allocated to each patient. All charges associated with the admission for each patient in the study will have costs allocated. This will be evaluated as an additional data point to compare the two arms of the study. No additional PHI will be collected.

Telephone Follow-Up

Subjects will also be contacted by phone by a research staff member at two different time points following their discharge from the hospital. These time points will be at 3 days (+2 days) and 30 days (+/- 3 days) following their discharge. At these time points a staff member will call a subject to obtain information about whether or not a patient has had recurrent bleeding and whether or not the patient had to be readmitted to a hospital or emergency room for

INVESTIGATOR STUDY PLAN - REQUIRED

recurrent bleeding. Please see attached form for telephone script that staff member will read along with particular questions that will be asked.

No more than three attempts will be made at each time point to reach the subject. If a message is left, it will be "Hello, this is [name] calling from UMass looking to speak with [subject]. Please call back at [number] at your earliest convenience. Thank you."

11) Data and Specimen Banking*

N/A – no data banking.

12) Data Management*

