Subjects will be only providing health information to the investigators in this study. They will be offered an opportunity to ask any questions they have regarding this study. All information that will be used for analysis in this study that utilizes patient health information will be password-encrypted and de-identified. HIPAA Authorization to Disclose will be obtained from subjects prior to enrollment in the study.

28) Compensation for Research-Related Injury

In the unlikely event of a research-related injury, subjects or their insurance will be responsible for coverage.

The only complication of capsule endoscopy, apart from inability of the patient to swallow the device, is true capsule retention [>> 2 weeks of retention] with or without obstruction. In this case it is the underlying disease causing the problem and the management would be covered by the patient's insurance.

29) Economic Burden to Subjects

None is anticipated from participating in the study. All costs associated with the emergency department stay, hospital admission and associated testing (including but not limited to endoscopy procedures) will be paid by the subject or insurance and the subject will be responsible for all co-pays, deductibles, etc. These are all standard of care procedures.

The patients recruited to be subjects in this study would most likely require admission to the hospital or the clinical decision unit until a thorough evaluation is completed to determine the source of bleeding. This is a clinical decision that will be made regardless of participation in this study, based on the clinical judgment of the attending physician in the emergency department.

For those in the early capsule group, the cost of using the prokinetic medications (if necessary) will also be paid by the subject or insurance as this is part of the standard of care procedures for their emergency department admission and assessment. Any subsequent intervention will be billed to the subject or insurance.

INVESTIGATOR STUDY PLAN - REQUIRED

The cost of the video capsule and its reading, both for the early capsule group and any subject in the standard of care group who receives a video capsule, will be paid for by the study and not billed to the subject or insurance.

30) Consent Process

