PUBLISH DATE JUNE 20, 2018

STATISTICAL ANALYSIS PLAN

TITLE: A comparison of early deployment of a video capsule (Endocapsule EC-10: Olympus Tokyo. Japan) in the Emergency Department versus conventional work-up of non-hematemesis gastrointestinal bleeding [NHGIB].

NCT02442830

[name], PHD, PRINCIPAL INVESTIGATOR

STATISTICAL ANALYSIS PLAN

Study outcomes:

The primary outcome for this study was the rate of localization of bleeding during hospitalization. Localization of bleeding was defined as identification of blood or identification of a lesion with high-risk stigmata of recent hemorrhage (SRH). Secondary outcomes included, overall rate of localization of bleeding by the end of admission, anatomic location of bleeding or the bleeding source, rate of endoscopic therapy, rate of readmission, rate of diagnosis of vascular lesions (defined as Dieulafoy's lesions or angioectasias), rate of re-bleeding within 30 days of discharge, rate of all-cause mortality within 30 days of hospitalization, cumulative direct hospital costs by the end of admission, and overall rate of identifying the etiologic diagnosis.

Sample size calculation:

The study was planned as a superiority trial and the estimated probability of localization of bleeding during hospitalization in the Early Capsule arm to be two times greater than that of the Standard of Care arm (i.e. estimated hazard ratio of 2.00). We found no prior studies similar to our methodology, so prior experience at our institution guided the estimation of effect. Power analysis revealed that for this effect size to be detected (80% chance) as significant at the 5% level, a sample of at least 72 patients (36 per group) would be required.

Statistical analysis:

Patient characteristics were described as means with standard deviation (SD) or as proportions. Time to localization and time to first procedure were described using medians with interquartile range (IQR). Hospital costs were described in US dollars (USD).

Independent variables selected for analysis included those previously suggested as prognostic indices for NHGIB. Variables chosen for analysis included gender, race, age, vital signs at admission, use of anticoagulants, use of non-steroidal anti-inflammatory drugs (e.g. aspirin and ibuprofen; NSAIDs), use of a P2Y₁₂ inhibitor (e.g. clopidogrel), factors that contribute to the Glasgow-Blatchford Score, and type of bleeding at admission (i.e. hematochezia, melena, or symptomatic anemia).

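### The SAP does not say whether the study-paid capsule and its reading count as direct hospital cost; a charge-based cost pull would plausibly omit them, and omission would favour the early-capsule arm

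*SAP*

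**What the plan says.** **SAP, Study outcomes.** One of the nine secondary outcomes is "cumulative direct hospital costs by the end of admission". The only other SAP text on cost is in Statistical analysis and gives the currency. There is no list of components and no rule for items funded by the study.

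**Protocol section 10, Review and Follow-Up.** Procedure costs are to be obtained from financial services, as fixed and variable costs for each patient. The section continues: "We will also collect the direct and indirect costs allocated to each patient". It then ties allocation to the charges: "All charges associated with the admission for each patient in the study will have costs allocated". On their use it says: "This will be evaluated as an additional data point to compare the two arms of the study".

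**Protocol section 29, Economic Burden to Subjects.** The cost of the capsule and its reading, for the early-capsule group and for any standard-of-care subject who has one, "will be paid for by the study and not billed to the subject or insurance". For care after the capsule in the early group the rule is the opposite: "Any subsequent intervention will be billed to the subject or insurance". Endoscopy and the rest of the admission are likewise charged to the subject or insurer.

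**Protocol section 10, Randomization and Procedure.** All early-capsule patients "will receive the video capsule. Only some of the patients in the" conventional group will. For conventional patients who need one, "the patients will be given the same Olympus video capsule that is used in the" early-capsule group.

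**The concern.** Cost data are described by reference to charges, while the device under test and its interpretation are not billed to patient or insurer. Nothing in either document says whether such an item creates a charge line in the hospital's accounts, or whether its cost is added afterwards. The SAP also narrows the protocol's range of cost types to direct hospital costs, and it does not say whether a device and reading bought by the study fall in that class. Two analysts could follow these documents and obtain different cost results.

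The gap would not be neutral between arms. An endoscopy avoided in the early arm would register as a saving, because endoscopy is billed. The capsule that made it avoidable might register as zero. The protocol's Background offers cost containment as a possible benefit of the strategy, so readers will look at the direction of the cost result.

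**Working it through.** The documents give no figure for the cost comparison, so there is nothing to reproduce. The check is of direction and relative size, conditional on the items being absent from the file.

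**Inputs**
- u: cost of one capsule plus its reading. Not given; left as a symbol.
- Capsule use in the early arm: 100% by design (Protocol section 10, Randomization).
- f: capsule use in the conventional arm. Not given directly; below 100% by design. There are two rough proxies:
  - 5–15%, the expected share of patients with small intestinal bleeding (Protocol section 10, conventional workup);
  - 36/336 = 10.7%, capsule use in an earlier emergency department series of all gastrointestinal bleeding (Protocol section 4).
- Patients per arm: 36 (SAP, Sample size calculation) or 80 (Protocol section 25).

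**Formula.** Omission lowers the mean cost by u × 1 in the early arm and by u × f in the conventional arm. The early-minus-conventional mean difference is therefore too low by

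u × 1 − u × f = u(1 − f).

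This is positive for every f below 100%, so the direction favours early capsule and needs no unit cost. The net number of uncosted capsules is n(1 − f), with n the number per arm.

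| f | Source | Shortfall in mean difference | Net capsules, 36 per arm | Net capsules, 80 per arm |
|---|---|---|---|---|
| 5% | proxy, lower end | 0.95u | 34.2 | 76.0 |
| 10.7% | proxy, earlier series | 0.89u | 32.1 | 71.4 |
| 15% | proxy, upper end | 0.85u | 30.6 | 68.0 |
| 30% | assumed | 0.70u | 25.2 | 56.0 |
| 50% | assumed | 0.50u | 18.0 | 40.0 |

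The two assumed rows are there because conventional use could exceed the proxies, given that the study also pays for capsules in that arm.

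The result applies to a difference in means. The effect on a rank test depends on the cost distribution, which the documents do not give, so none is computed.

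**The case against.** The strongest reply is that no document shows an omission. Section 29 answers who pays. An item not billed to the patient or insurer can still be charged to a study account and carry a cost in the hospital's system. Section 10 can be read as leaning towards inclusion: it speaks of procedure costs, and of fixed and variable costs tied to each patient, and capsule endoscopy is a procedure in this trial. This stands. A reader might infer that the cost comparison is biased; the documents support only that it may be. Section 32, which keeps the capsules in the study coordinator's office, fits handling outside ordinary hospital supply but does not establish it.

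Three further limits also stand:
- The values of f are proxies. One is a bleeding-site frequency, not capsule use. The other covers all gastrointestinal bleeding, whereas this trial concerns bleeding without hematemesis.
- The SAP does not name a test for cost. Its Wilcoxon sentence refers to continuous variables in general, so applying that test to cost is an inference. The protocol's data analysis plan (section 12) mentions t-tests on the dependent variables.
- Excluding a study-funded item can be a legitimate costing perspective if it is declared.

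None of this closes the gap. The perspective is not declared, and the only allocation rule given is tied to charges.

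**Conclusion.** The point holds in conditional form. The plan does not say whether the capsule and its reading are in the cost total, and a charge-based pull would plausibly leave them out. If so, the early-minus-conventional mean cost is understated by u(1 − f): about 0.85u to 0.95u on the documents' proxies, and 0.50u at an assumed f of 50%. This rests on every early-arm patient receiving a capsule as planned and on one unit cost serving both arms, which is reasonable because the capsule is the same.

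A reader might go further and conclude that most of the strategy's cost is missing, or that a cost saving would disappear. The documents support neither. The early strategy also includes the admission and any later procedures, and no cost of any kind is stated, so the capsule's share of the total is unknown. With no unit cost and no cost standard deviation, the dollar size and any effect on significance are unknown too.

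The primary outcome is unaffected. Cost is one of nine secondary outcomes in the SAP and is not among the endpoints in Protocol section 9. The change is worth making because it is cheap and removes a possible bias of known direction; it does not threaten the trial's main conclusion.

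**What to change.** 1. Ask financial services whether the cost file contains the capsule and its reading for recipients in each arm.
2. If it does, leave the data as they are and say so in the SAP.
3. If it does not, add one fixed unit cost, with a named source, for each recipient in either arm. Report the between-arm cost comparison with and without it, and state in the SAP which version is the main result.

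The cost is one query, one SAP sentence and, if the items are absent, one added term per recipient. Recipients should be identifiable from the procedure types and times already recorded under Protocol section 10. The downsides are that a unit cost must be obtained from outside these documents and that the early-arm cost result may become less favourable.

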VERSION DATE APRIL 22, 2016

TITLE: A comparison of early deployment of a video capsule (Endocapsule EC-10: Olympus Tokyo. Japan) in the Emergency Department versus conventional work-up of non-hematemesis gastrointestinal bleeding [NHGIB].

NCT02442830

[name], PHD, PRINCIPAL INVESTIGATOR

INVESTIGATOR STUDY PLAN - REQUIRED

1) Title

A comparison of early deployment of a video capsule (Endocapsule EC-10: Olympus Tokyo. Japan) in the Emergency Department versus conventional work-up of non-hematemesis gastrointestinal bleeding [NHGIB].

2) IRB Review History*

Not applicable.

3) Objectives*

The objectives of this study are to test whether there are statistically significant differences between the conventional workup of NHGIB by endoscopy [upper, lower and other tests], compared with deployment of a video capsule VCE as the first test followed by the most appropriate endoscopic procedure based on VCE findings, if needed. We propose to examine differences in time to diagnosis, reduction in numbers of procedures, and length of stay between a conventional workup protocol and our proposed protocol of early capsule endoscopy deployment.

4) Background*

After 40 years of considering gastrointestinal bleeding as upper or lower and largely ignoring the small intestine, there is accumulating evidence that the conventional approach to the assessment of NHGIB could be improved by early deployment of a video capsule as the first diagnostic test. Currently, video capsule endoscopy is considered the gold standard as the diagnostic test for small intestinal bleeding. In a recent study at UMass of 336 patients who presented to the ED with complaints of gastrointestinal bleeding 36 patients (10.7%) were given a video capsule during their stay.¹

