In patients with hematemesis, upper endoscopy remains the diagnostic and therapeutic modality of choice. However patients with melena and hematochezia may benefit from early VCE since both signs and symptoms provide poor localization as to the origin of bleeding. Data from our previous study suggests that the ingestion of a video capsule in the emergency department could quickly and non-invasively provide clinicians accurate data as to the origin of the bleeding. This information could provide a guide to further management of the patient. Video capsule endoscopy is able to visualize bleeding in the esophagus, stomach, duodenum, small intestine and right colon, thereby eliminating the guess work of deciding which endoscopic approach to use.

At UMass, we have shown that of the 36 patients who received a video capsule, 26 (72.2%) had diagnostic studies (i.e. bleeding was identified). In comparison, 152 patients required upper endoscopy (of which 52.9% were diagnostic) and 64 patients required colonoscopy (of which 47%

INVESTIGATOR STUDY PLAN - REQUIRED

were diagnostic). Of those 26 patients with diagnostic capsule studies, 13 also required upper endoscopy, 1 required a colonoscopy, and 4 required both a colonoscopy and endoscopy. It is important to recognize, however, that often capsule studies are performed AFTER upper endoscopy and colonoscopy and performed and are negative. This sequence is the conventional work up of bleeding. Despite being performed later in the hospital course of our patients, capsule studies have a high diagnostic yield. In reality VCE is used uncommonly in acute bleeding because it is rarely considered in the context of acute GI bleeding

In this study, we propose the approach of using the video capsule as the first diagnostic test PRIOR to colonoscopy and endoscopy; this may lead to a shortened time to diagnosis, a reduction in length of stay, and a reduction in numbers of procedures due to early, accurate localization of the source of bleeding. All of these components could result in better quality of care and cost containment.^{1,2} Further, it is known that 80% of patients stop bleeding spontaneously. Thus the earlier they are examined the more likely the origin of the bleeding is likely to be found

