Univariate analyses involved Wilcoxon-Rank sum tests for continuous variables and Chi-square or Fisher's Exact tests for binary variables. A Kaplan-Meier survival analysis with a Log-rank test compared the cumulative incidence of endoscopic localization of bleeding for the two groups. For multivariate analyses, independent variables with a difference at $p<0.10$ following univariate analysis or those noted to be unevenly distributed between the two cohorts were included as covariates. A p -value of less than 0.05 was significant. Statistical analysis was performed using STATA 13.

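### A doubled localization probability, a hazard ratio of 2.00 and 80% power from 72 patients cannot all hold, and the SAP states no event count or control-arm rate

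*SAP*

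**What the plan says.** The SAP's Sample size calculation section describes a superiority trial. It sets the probability of localization during hospitalization in the Early Capsule arm at "two times greater than that of the Standard of Care arm (i.e. estimated hazard ratio of 2.00", and concludes that "a sample of at least 72 patients (36 per group) would be required" for 80% power at the 5% level. The effect is attributed to institutional experience. The section gives no formula, sidedness, required number of events or control-arm localization rate.

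The Statistical analysis section names the test: "A Kaplan-Meier survival analysis with a Log-rank test compared the cumulative incidence of endoscopic localization of bleeding for the two groups".

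The protocol gives no per-patient localization rate for the conventional arm. Its Background reports per-procedure yields from a retrospective series of "336 patients who presented to the ED with complaints of gastrointestinal bleeding": "152 patients required upper endoscopy (of which 52.9% were diagnostic) and 64 patients required colonoscopy", the latter with a 47% yield. Protocol section 10 says the conventional workup "could include upper endoscopy, colonoscopy, and additional capsule or small bowel enteroscopy", so a control patient may have more than one chance of localization. It also plans for early-capsule patients without a finding: "If the capsule study is not diagnostic and no blood is seen in the GI tract".

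**The concern.** A log-rank test draws its power from events, here localizations, and not from patients enrolled. A patient count follows from a hazard ratio only once the fraction of patients expected to have the event is assumed, and the SAP assumes none. Its figure of 72 is also almost exactly the number of events one standard formula requires, which suggests, without proving, that events were taken as patients.

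Separately, a doubled cumulative probability and a hazard ratio of 2.00 are different effects, so a reader cannot tell which one the trial was sized to detect.

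This is the only sample-size justification for the SAP's primary outcome. The protocol's 160 was calculated for a different primary endpoint, time to diagnosis, from means and standard deviations. If enrolment ended near the SAP's minimum, a non-significant result could be read as coming from an adequately powered trial when it did not.

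**Working it through.** **Inputs.** From the SAP: hazard ratio (HR) 2.00, 80% power, 5% level, 36 per arm, log-rank test. Assumed here: a two-sided test (the SAP does not say), proportional hazards, and the same follow-up window in both arms. Write p_C and p_E for the proportions localized in the control and early-capsule arms.

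**Step 1. Reproduce 72.** With z = 1.96 and 0.8416, (1.96 + 0.8416)² = 7.849.
- Freedman: 7.849 × [(2 + 1)/(2 − 1)]² = 7.849 × 9 = 70.6 events, or 36 per arm and 72 in total after rounding.
- Schoenfeld: 4 × 7.849 / (ln 2)² = 65.3 events.

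So 72 is reproduced as a Freedman event count. As a patient count it would require essentially every patient to be localized.

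**Step 2. Control rate at which 72 patients give 80%.** Under proportional hazards, p_E = 1 − (1 − p_C)². Expected events are D = 36 × (p_C + p_E) = 36 × (3p_C − p_C²). Setting D = 65.3 gives p_C = 0.841; setting D = 70.6 gives p_C = 0.964.

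**Step 3. Compare with a doubled probability.** Doubling requires p_C ≤ 50%. At p_C = 50%, HR 2.00 gives p_E = 75% and D = 36 × 1.25 = 45.
- Freedman power: Φ(√45/3 − 1.96) = 61%.
- Schoenfeld power: Φ(√45 × ln 2/2 − 1.96) = 64%.

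Even crediting the trial with the literal doubling of 50% vs 100%, D = 36 × 1.5 = 54, and power at HR 2.00 is 69% or 72%. At the 84–96% needed for 80% power, doubling would exceed 100%. This conflict uses no outside rate.

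**Step 4. Doubling is not HR 2.00.** HR 2.00 implies p_E = 2p_C − p_C², always below 2p_C. Conversely, doubling implies HR = ln(1 − 2p_C)/ln(1 − p_C), always above 2: 2.41 at 25% vs 50%, 2.67 at 32.5% vs 65%, 2.86 at 36.1% vs 72.2%.

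**Step 5. Size of the shortfall at HR 2.00, 36 per arm.** The simulated column uses 8,000 log-rank trials per rate with exponential times and a common window. Its Monte Carlo standard error is about half a percentage point (√(0.62 × 0.38/8,000) = 0.0054).

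| Control rate | Expected events | Freedman | Schoenfeld | Simulated |
|---|---|---|---|---|
| 32.5% | 31.3 | 46% | 49% | 48% |
| 47% | 42.8 | 59% | 62% | 62% |
| 50% | 45.0 | 61% | 64% | 65% |
| 52.9% | 47.1 | 63% | 66% | 67% |
| 60% | 51.8 | 67% | 70% | 71% |
| 75% | 60.8 | 74% | 77% | 77% |
| 85% | 65.8 | 77% | 80% | 79% |

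The 47% and 52.9% are the Background's per-procedure yields, used only as a proxy. The 75% assumes both procedures in every patient, with independent results: 1 − 0.471 × 0.53 = 0.75. The other rates are assumptions. Patients needed for 66–71 events are 112–120 at 47%, 106–114 at 50% and 79–85 at 75%.

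**Step 6. The doubled-proportion reading.** For a two-sided chi-square test without continuity correction, 36 per arm gives 59% power for 25% vs 50%, 73% for 30% vs 60%, 80% for 32.5% vs 65% and 88% for 36.1% vs 72.2%. The two-proportion formula returns 35.9 per arm for 32.5% vs 65%. This reading can support 72, but only with a control rate of at least about 32.5%, which the SAP does not state, and with a hazard ratio of about 2.67 or more.

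**The case against.** The strongest reply is that 72 is not miscalculated. It reproduces from HR 2.00, and the parenthesis merely defines loose wording, so the planned effect is the hazard ratio and the talk of doubling can be set aside. That would leave an unreported event fraction. The reading is fair, but it does not rescue the 80%: with HR 2.00 alone, 72 patients still need 84–96% control localization.

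Sidedness is not stated. One-sided at 5%, 72 patients give 70–73% power at 47% control and 83–86% at 75%, reaching 80% from about 59–66%. That stands as a caveat to the 59–77% range. It does not remove the contradiction, because doubling is impossible at those rates and power at 50% control is only 72–75%. The match to 72 also arises from the two-sided formula.

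The control rates are proxies: per-procedure yields in selected patients from a series of all gastrointestinal bleeding. The range also spans two formulas; Freedman alone gives 59–74% and Schoenfeld alone 62–77%. Both points stand, and neither formula reaches 80% in that range. The protocol sentence on non-diagnostic capsule studies concerns the early-capsule pathway, so it says little about the control rate. Proportional hazards and equal follow-up are also simplifications, since the capsule arm is hoped to have shorter stays.

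Finally, 72 is a minimum and the protocol allows up to 160. With 80 per arm, D = 80 × (3p_C − p_C²) is 95 at 47% and 135 at 75%, giving 90–98% power. The harm is therefore conditional on enrolment ending near 72.

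**Conclusion.** The concern holds. A doubled probability, HR 2.00 and 80% power from 72 patients are incompatible at every control rate, on two-sided testing and proportional hazards, without relying on any proxy. At the highest control rate that doubling allows, 50%, power at HR 2.00 is 61–64% rather than 80%. Over assumed control rates of 47–75% it is about 59–77%, and that range is illustrative. The figure of 72 matches a Freedman event count, but whether events were mistaken for patients cannot be established from the documents. A doubled-proportion design of about 32.5% vs 65% would justify 36 per arm, but it is not the design the SAP states.

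**What to change.** In the SAP's Sample size calculation section, remove the equivalence between a doubled probability and the hazard ratio, name the method and the sidedness, and say which effect was planned.

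- **If HR 2.00:** state the required events (about 66 by Schoenfeld or 71 by Freedman), the assumed control-arm localization by discharge and its source, and the proportions HR 2.00 then implies (for example 50% vs 75%). Replace the claim of 80% with the power 72 patients give over a stated range of control rates, labelled as assumptions: roughly 59–77% for 47–75%, two-sided.
- **If a doubled proportion:** state both proportions (80% with 36 per arm needs about 32.5% vs 65%) and delete the "estimated hazard ratio of 2.00".

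The section reports a calculation already made. If its original assumptions cannot be recovered, it should say so and not present rates chosen later as the planning basis.

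The cost is SAP wording only: no added patients, visits or data, and no change to the protocol's ceiling of 160. Under HR 2.00 the stated power becomes less favourable.
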